11.3.5 Electrocardiogram

After each recording of a simultaneous 12-lead resting ECG, a copy will be printed and assessed by an investigator for at least the following parameters: heart rate, heart rhythm, P pulmonale, right axis deviation, RV hypertrophy, RV strain, right bundle branch block, P-R interval, QRS duration, QT interval and QTc interval. [8]

At visits A1 and MPV3 triplicate ECG recordings will be performed before IMP intake as well as 4 and 8 hours after IMP intake. Painful procedures, like drawing blood, should always be performed after ECG recordings (not before).

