10. In scleroderma patients only.
11. Blood pressure and heart rate will be measured in supine position (two measurements) and afterwards in standing position (one measurement).
12. At A1 and MPV3 blood pressure and heart rate (two measurements in supine and one measurement in standing position) will be measured before IMP intake as well as 4, 8 and 24 hours after IMP intake.
13. Two baseline tests, separated by an interval of at least 30 minutes.
14. Blood samples will be taken prior to IMP intake.
15. 24-hour urine collection will start on the day before the respective visit.
16. Right heart catheterisation and arterial blood gas analysis have to be performed before IMP intake.
17. Applicable in all patients who will not participate in the extension study as well as in patients who discontinued early.
18. At A1 and MPV3 triplicate ECGs recordings will be performed before IMP intake, 4 and 8 hours after IMP intake. At EDV only one ECG recording will be performed.
19. Down-titration can be performed at a scheduled visit or an unscheduled visit (on-site visit or telephone contact) during the dose finding period.
20. 6-MWT has to be performed after arterial blood gas analysis but before right heart catheterisation and IMP intake.
21. Arterial blood gas analysis has to be performed before right heart catheterisation.
22. Right heart catheterisation will only be performed if no results which were measured at the study site from within 90 days before V1 are available.

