## 4.7 Baseline Value

### Baseline value

The baseline value for a variable is defined as the last non-missing value collected before the first IMP intake, unless otherwise specified.

See section 5.4.1 Exposure to IMP for definition of first IMP intake.

**Absolute change from baseline** will be calculated as

$$\text{Absolute Change from Baseline at Visit } X = \text{Value at Visit } X - \text{Baseline Value}$$

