## 5.6.5 12-Lead Electrocardiogram (ECG) Data

A simultaneous 12-lead resting electrocardiogram (ECG) will be collected at screening (V1), A1, A3/B3/C3/D3, MPV1, MPV2, MPV3/EDV and FUV2. At visits A1 and MPV3 triplicate ECG recordings will be performed at following time points - before IMP intake as well as 4 and 8 hours after IMP intake. At EDV only one ECG recording will be performed. For patients enrolled under protocol version final 1.0, ECG assessments were only collected once at visits V1, A3/B3/C3/D3, MPV1, MPV3/EDV.

Following parameters will be assessed:

- Heart rate (bpm)
- P-R interval (msec)
- QRS duration (msec)
- QTcF interval (msec)
- QT interval (msec)
- P pulmonale
- Right axis deviation
- RV hypertrophy
- RV strain
- Right bundle branch block
- Heart rhythm (normal, abnormal)

For patients enrolled under protocol version final 1.0, heart rhythm was not collected.

Clinical significance (yes/no) of any abnormal ECG data findings will be assessed by the investigator. Parameter values without a clinical significance evaluation will be considered as “Normal”, and values with “No” or “Yes” clinical significance evaluations will be considered as “NCS Abnormal” and “CS Abnormal”, respectively.

Where multiple ECG recordings are performed within a visit or timepoint, ECG parameters will be summarised as follows. For numeric parameters, the mean of collected values will be used in summaries. For abnormality assessments, the worst value within the visit/timepoint will be used.

To evaluate the short-term effects of the IMP on ECG parameters, the absolute change from the pre-dose value within the corresponding visit will be calculated for each parameter at visits A1 and MPV3. Additionally, the difference in the within-visit changes will be evaluated for each corresponding timepoint between visits MPV3 and A1.

The following statistical output will be provided:

Table 15.3.5.1.1 Summary of ECG Assessments by HTD – Safety Set

Table 15.3.5.1.2 Summary of ECG Assessments – Safety Set

ECG parameters will be summarised including change from baseline at each visit by HTD and overall.

Table 15.3.5.2.1 Summary of Short-Term IMP Effect on ECG Assessments by HTD – Safety Set

Table 15.3.5.2.2 Summary of Short-Term IMP Effect on ECG Assessments – Safety Set

The observed values and absolute changes from the pre-dose value will be summarised for each vital sign parameter at each timepoint by HTD and overall.

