Table 15.3.5.3.1 Summary of Change in Short-Term IMP Effect on ECG Assessments by HTD – Safety Set

Table 15.3.5.3.2 Summary of Change in Short-Term IMP Effect on ECG Assessments – Safety Set

The changes from pre-dose values and the differences in changes from pre-dose values will be summarised between corresponding timepoints at visits A1 and MPV3 by HTD and overall.

Table 15.3.5.4.1 Incidence of ECG Abnormalities – Safety Set

Number and percentage of patients with Not CS abnormal and CS abnormal ECG parameters assessments will be displayed by HTD and overall. Percentage will be based on the number of patients at specified visit.

Table 15.3.5.4.2 Shift Table of ECG Abnormalities – Safety Set

Shift tables showing changes in the number and frequency of patients in not CS abnormal and CS abnormal categories between baseline and MPV3/EDV will be provided. The worst abnormality assessment collected during MPV3/EDV will be selected for each patient. Percentage will be based on the number of patients in the safety set.

Table 15.3.5.4.3 Shift Table of Within-Visit ECG Abnormalities – Safety Set

Shift tables showing changes in the number and frequency of patients in not CS abnormal and CS abnormal categories between the pre-dose measurement and each post-dose measurement at each visit.

The worst abnormality assessment collected during the corresponding timepoint will be selected for each patient. Percentage will be based on the number of patients in the safety set.

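### In patients enrolled after protocol version 1.0 who reach MPV3, the ECG shift table sets the worst of up to nine recordings against a baseline of at most three, so it leans towards abnormal with no drug effect

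*SAP*

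**What the plan says.** SAP 5.6.5 defines Table 15.3.5.4.2 as a shift table across "not CS abnormal and CS abnormal categories between baseline and MPV3/EDV will be provided". For the later side of the shift the rule is "The worst abnormality assessment collected during MPV3/EDV will be selected for each patient".

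The number of recordings comes from the same section, which says of MPV3 and of A1 alike: "triplicate ECG recordings will be performed at following time points - before IMP intake as well as 4 and 8 hours after IMP intake". Protocol 11.3.5 and footnote 18 of the schedule (SAP 1.2) agree. At an EDV a single ECG is taken. Patients enrolled under protocol version 1.0 had one ECG at V1 and one at MPV3/EDV.

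For baseline, SAP 4.7 takes "the last non-missing value collected before the first IMP intake, unless otherwise specified". For repeated recordings, SAP 5.6.5 adds: "For abnormality assessments, the worst value within the visit/timepoint will be used". Nothing in 5.6.5 equalises the number of recordings on the two sides of this table.

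**The concern.** The worst of several readings depends on how many readings there are. If a patient's ECG is flagged abnormal now and then, nine looks will catch it more often than three, and three more often than one. A shift table with unequal numbers of looks therefore moves patients in one direction even when nothing has changed.

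The A1 recordings at 4 h and 8 h follow the first dose, so they cannot count towards baseline. That leaves at most the pre-dose triplicate. The pooled table then mixes three comparisons: 3 v 9 (enrolled after version 1.0 and reached MPV3), 3 v 1 (enrolled after version 1.0, EDV) and 1 v 1 (version 1.0).

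Clinically relevant ECG change is a named secondary safety endpoint (SAP 2.2.2.1; Protocol 13.1.2.1), and the study has no control arm in which the same imbalance would show. Worsening would be overstated among patients followed to MPV3 and understated among those who stopped early, a group of particular interest for safety.

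**Working it through.** **Inputs from the documents**
- MPV3: 3 time points × 3 recordings = 9 (SAP 5.6.5; Protocol 11.3.5).
- Baseline: the A1 pre-dose triplicate, 3 recordings (SAP 4.7 with the worst-within-timepoint rule in 5.6.5).
- EDV: 1 recording. Version 1.0: 1 at V1 and 1 at MPV3/EDV (SAP 5.6.5).
- Planned N = 32 (Protocol 13.3; SAP 2.6), used only to turn percentages into patients.

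The plan gives no false-shift rate to reproduce.

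**Assumed inputs.** The documents give neither of these:
- p, the chance that one recording is flagged for a given parameter, is the same before and on drug. The main value is 5%, with a range of 2% to 10%.
- ρ, the within-patient correlation between flags, runs from 0 to 0.9.

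**Direction.** The MPV3 pre-dose triplicate is a subset of the nine. With no change over time it is as likely to contain a flag as the A1 pre-dose triplicate. Adding six recordings can only raise that chance, so the net shift is towards abnormal unless repeat readings agree perfectly. This does not depend on p or ρ.

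**Size.** Let Q(m) be the chance of no flag in m recordings. Under a beta-binomial with a = p(1−ρ)/ρ and b = (1−p)(1−ρ)/ρ,

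Q(m) = ∏ (b+i)/(a+b+i), i = 0 to m−1; for ρ = 0, Q(m) = (1−p)^m.

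With m0 baseline and m1 later recordings:
- normal to abnormal = Q(m0) − Q(m0+m1)
- abnormal to normal = Q(m1) − Q(m0+m1)
- net = Q(m0) − Q(m1)

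Worked case, p = 0.05 and ρ = 0.25: a = 0.15, b = 2.85.
- Q(3) = (2.85/3)(3.85/4)(4.85/5) = 0.887; Q(9) = 0.793; Q(12) = 0.766.
- Normal to abnormal = 0.887 − 0.766 = 12.1%.
- Abnormal to normal = 0.793 − 0.766 = 2.7%.
- Net = 0.887 − 0.793 = 9.4%, or 3.0 of 32.

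Results for 3 v 9, no drug effect, per ECG parameter, p = 5%:

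| ρ | Normal to abnormal | Abnormal to normal | Net, if all 32 were 3 v 9 |
|---|---|---|---|
| 0 | 31.7% | 9.0% | +7.3 |
| 0.25 | 12.1% | 2.7% | +3.0 |
| 0.5 | 5.6% | 1.2% | +1.4 |
| 0.6 | 4.0% | 0.8% | +1.0 |
| 0.9 | 0.8% | 0.2% | +0.2 |

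Over p = 2% to 10%, the net excess is +1.1 to +4.4 of 32 at ρ = 0.3, +0.4 to +1.9 at ρ = 0.6, and +0.1 to +0.4 at ρ = 0.9.

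**The other comparisons (p = 5%)**
- EDV, 3 v 1: 2.0% to abnormal against 7.7% back at ρ = 0.3; 0.8% against 3.9% at ρ = 0.6. The lean is reversed.
- Version 1.0, 1 v 1: equal in both directions, net 0.
- Matched 3 v 3: 5.7% each way at ρ = 0.25 and 2.8% each way at ρ = 0.5, net 0 for every p and ρ.
- If last value is read as one recording, so 1 v 9: 14.7% against 0.8% at ρ = 0.3.

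**The case against.** The strongest reply has four parts.

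1. **Worst on-treatment is a recognised conservative safety summary.** The study is descriptive, no test is planned on this table, and the SAP states the selection rule openly. This stands as a reason to keep the figure. It does not justify using it as one side of a shift whose other side has fewer looks.

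2. **Neighbouring outputs already cover much of the ground.** Table 15.3.5.4.3 gives matched shifts from pre-dose to each post-dose time point within a visit, worst of three against worst of three. Numeric ECG parameters are averaged over recordings, so worst-of-n inflation does not arise in their summaries. Both points stand. However, neither output pairs A1 pre-dose with MPV3 pre-dose for the abnormality assessments, and that pairing is the baseline-to-MPV3 question.

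3. **The size is assumed.** This also stands. Five of the eleven listed parameters are morphological (P pulmonale, right axis deviation, RV hypertrophy, RV strain, right bundle branch block). Where such a finding is fixed, repeat readings agree closely and the excess is a fraction of a patient. The model also uses one correlation both within a visit and between visits, which is a simplification. The ρ = 0 row is an extreme, not an expectation.

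4. **Not every patient is affected.** A reader might infer that every completer is compared nine against fewer. SAP 5.6.5 rules that out for version 1.0 patients, and the documents do not say how many there were.

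A reader might also infer that Table 15.3.5.4.1 gives A1 and MPV3 nine chances to be abnormal against one at other visits. The text does not establish this: the rule refers to visit/timepoint, and the table shell, which would settle it, is in an appendix that is not reproduced.

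**Conclusion.** The concern holds for one table and for identifiable patients. Among those enrolled after version 1.0, Table 15.3.5.4.2 leans towards abnormal in patients who reach MPV3 and towards normal in patients seen at an EDV. The direction follows from the recording counts. The size is conditional: at 5% flagged per recording it ranges from about three excess patients of 32 per parameter at correlation 0.25 to about 0.2 at correlation 0.9. It matters for intermittent findings and hardly at all for fixed ones. The actual excess also scales with the unknown share of patients who are 3 v 9.

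Two stronger conclusions are not supported. The documents do not show that the ECG abnormality outputs as a whole are biased, because the within-visit shifts are matched and the numeric summaries use means. Nor does the SAP present this table as an estimate of drug effect. The point is that, without a control arm, a reader cannot separate a drug-related shift from the extra recordings.

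**What to change.** In SAP 5.6.5:
- Make the main baseline-to-MPV3 shift in Table 15.3.5.4.2 the worst of the A1 pre-dose triplicate against the worst of the MPV3 pre-dose triplicate. State that ECG abnormality baseline is formed in this way.
- Show EDV patients and version 1.0 single-recording patients as separate rows.
- Keep the worst-of-visit result at MPV3 as a labelled supplementary row, with a footnote giving the number of recordings on each side.
- Leave Table 15.3.5.4.3 as it is. It already gives the matched 4 h and 8 h shifts and need not be duplicated.
- If the shell for Table 15.3.5.4.1 collapses A1 and MPV3 to one row per visit, present those two visits by time point.

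No new data are needed. The cost is a few sentences of SAP text and one re-cut table (two if the last item applies), with small cells in the separate rows. The conservative worst-of-visit figure is kept.

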#### Listing 16.2.4.5 Electrocardiogram – Enrolled Set

Values of simultaneous 12-lead resting electrocardiogram tests will be listed.

### **5.6.6 Physical Examination Findings**

Physical examinations will be performed at Visit 1, visits A3/B3/C3/D3, MPV1, MPV2, MPV3/EDV on relevant body systems (appearance, skin, eyes, ears-nose-throat, lungs-chest, heart, abdomen, extremities, other). Clinical significance (yes/no) of any abnormal physical examination findings and specification of clinically significant abnormality findings will be assessed by the investigator.

The following statistical output will be provided:

#### Table 15.3.6 Summary of Physical Examination Findings – Safety Set

Number and percentage of patients with not CS abnormal and CS abnormal physical examinations findings will be displayed at each visit by HTD and overall. Percentage will be based on the number of patients at the specified visit.

#### Listing 16.2.4.6 Physical Examinations – Enrolled Set

Values of physical examination will be listed.

### **5.6.7 Number of Digital Scars**

Number of digital scars will be documented in patients with scleroderma only.

At Visit 1 the investigator will document the number of existing digital scars at the fingers and toes. At visits A3/B3/C3/D3, MPV1, MPV2 and MPV3/EDV the investigator will examine fingers and toes of the patient and will document the number of digital scars. Additionally, the clinical examination will be supported by interviewing the patient.

For patients enrolled with protocol version 1.0 the investigator documented only the number of new scars at post-baseline visits, therefore the total number of scars will be derived adding number of scars at baseline and new scars.

The following statistical output will be provided:

#### Table 15.3.7.1 Summary of Scleroderma Scarring by HTD – Safety Set

#### Table 15.3.7.2 Summary of Scleroderma Scarring – Safety Set

The default summary statistics of number of digital scars will be presented by HTD and overall at each visit. The absolute change from baseline will be presented as well.

#### Listing 16.2.4.7 Number of Digital Scars – Enrolled Set

Number of scars will be listed by visit.

### **5.6.8 Modified Rodnan Skin Score (mRSS)**

The mRSS is a measure of skin thickness and is used as an outcome measure for scleroderma.

The score consists of an evaluation of patient's skin thickness rated by clinical palpation using a scale from 0 to 3 (0=normal skin; 1=mild thickness; 2=moderate thickness; 3=severe thickness) for each of 17 surface anatomic areas of the body: face, anterior chest, abdomen, (right and left separately) fingers, forearms, upper arms, thighs, lower legs, dorsum of hands and feet. These individual values are added, and the sum is defined as the total skin score.

The investigator will document the total skin score at Visit 1 and visit MPV3/EDV.

The following statistical output will be provided:

Table 15.3.8.1 Summary of mRSS by HTD – Safety Set

Table 15.3.8.2 Summary of mRSS – Safety Set

The default summary statistics of modified Rodnan score will be presented by HTD and overall at each visit. The absolute change from baseline will be presented as well.

Listing 16.2.4.8 Modified Rodnan Skin Score – Enrolled Set

Values of mRSS will be listed.

## 6 DATA REVIEW

The aims of the Data Review (DR) are:

- to identify major/minor protocol deviations, that may affect the pharmacokinetic or pharmacodynamic outcomes, or the treatment of the patients
- to identify impacts of the COVID-19 pandemic on the study conduct
- to solve any outstanding issues in the SAP
- to discuss any open data issues

The DR will be performed after data entry and following a database lock. All decisions made during the DR will be documented in the DR report before the closure of the database.

An appropriate clinical study team, including a physician, will review potential protocol deviations and relevant information regarding those deviations to determine a possible impact on pharmacokinetic endpoints. The status, major or minor, of each protocol deviation will be documented in the DR report. A patient may have one or more major protocol deviations resulting in the exclusion of that patient from the PKS set.

Protocol deviations will, if possible, be validated against data recorded in the eCRF. Where an answer for an inclusion/exclusion tick box differs from the algorithmic check of the criteria, the algorithmic check will overrule the tick box.

Additionally, protocol deviations will be reviewed by the medical monitor and will be categorized according to their impact on the PK analysis into following groups: major, minor and case by case decision.

Protocol deviations of the following categories and respective data listings will be reviewed during the DR.

### Inclusion Criteria

No.	Inclusion Criteria Deviation	Major/ Minor/ Case by case review
PD#01.	Male or female patients aged 18 to 75 years, inclusive.	Case by case
	Protocol Versions Final 1.0 and 2.0: Male or female patients aged 18 to 65 years.	
PD#02.	Able to comprehend and willing to sign an informed consent form (ICF).	Major
PD#03.	Diagnosis of PAH (pulmonary arterial hypertension WHO Group 1) documented by RHC with a mPAP $\geq$ 25 mmHg, a PAWP $\leq$ 15 mmHg and a PVR > 3 WU [8,9]: a) Idiopathic, in non-vasoreactive patients b) Heritable: Bone morphogenetic protein receptor type II (BMP2) mutation and other mutations, in non-vasoreactive patients c) Drugs and toxin induced, in non-vasoreactive patients d) Associated with connective tissue disease e) Associated with simple congenital defects (atrial septal defect and/or ventricular septal defect) if closed > 12 months before inclusion.	Case by case
PD#04.	Added in Protocol Version Final 3.0: The patient's last right heart catheterisation results, which were measured at the study site, must not be older than 90 days before V1 (will be considered as baseline value). Otherwise a right heart catheterisation has to be performed as part of the study at visit A1.	Minor

No.	Inclusion Criteria Deviation	Major/ Minor/ Case by case review
PD#05.	WHO functional class II or III as judged by the investigator.	Case by case
PD#06.	Stable treatment with at least one of the following approved PAH therapies for at least 90 days prior to V1: Ambrisentan, Bosentan, Macitentan, Riociguat, Selexipag, Sildenafil, Tadalafil, Epoprostenol intravenous, Iloprost inhaled or Treprostinil intravenous or subcutaneous.	Case by case
	Protocol Version Final 1.0: Stable treatment with at least one of the following approved oral PAH therapies within 3 months before V1: Ambrisentan, Bosentan, Macitentan, Riociguat, Selexipag, Sildenafil or Tadalafil.	
PD#07.	Added in Protocol Version Final 3.0: For women: Agree not to donate ova from the time of informed consent until 30 days after the last IMP intake. For men: Agree not to donate sperm from the time of informed consent until 90 days after the last IMP intake.	Minor

### Exclusion Criteria

No.	Exclusion Criteria Deviation	Major/ Minor/ Case by case review
PD#08.	Contraindication to zamicastat, i.e. known hypersensitivity to ingredients of zamicastat formulation.	Minor
PD#09.	Two or more consecutive measurements of SBP < 95 mmHg or DBP < 50 mmHg measured at V1.	Minor
	Protocol Version Final 2.0 Two or more consecutive measurements of SBP < 95 mmHg or DBP < 50 mmHg.	
	Protocol Version Final 1.0: Persistent hypotension defined as SBP < 95 mmHg or DBP < 50 mmHg.	
PD#10.	Uncontrolled diabetes mellitus with HbA1c $\geq$ 8.5% within the last three months or at screening.	Minor
	Protocol Version Final 1.0: Uncontrolled diabetes mellitus.	
PD#11.	PAH WHO Group 1 due to portal hypertension, human immunodeficiency virus (HIV) infection and schistosomiasis.	Case by case
PD#12.	Any disease known to cause pulmonary hypertension other than PAH WHO Group 1.	Case by case
	Protocol Version Final 1.0: Any disease known to cause pulmonary hypertension other than PAH WHO Group 1 e.g. obstructive lung diseases, parasitic disease affecting the pulmonary system, sickle cell anaemia, left heart disease.	
PD#13.	Added in Protocol Version Final 2.0:	Case by case

No.	Exclusion Criteria Deviation	Major/ Minor/ Case by case review
	Obstructive lung disease: Forced Expiratory Volume in 1 second/Forced Vital Capacity (FEV1/FVC) < 60% and FEV1 < 60% of predicted value after bronchodilator administration.	
PD#14.	Restrictive lung disease: Total Lung Capacity (TLC) < 70% of predicted value, as demonstrated and documented by previous spirometry data which, in the opinion of the investigator, represent the clinical state of the patient at the time of the screening visit.	Case by case
	Added in Protocol Version Final 2.0:	
	Restrictive lung disease: Total Lung Capacity (TLC) < 70% of predicted value.	
PD#15.	History of moderate to severe hepatic impairment (Child-Pugh B and C).	Case by case
PD#16.	Estimated glomerular filtration rate (eGFR) < 30 mL/min/1.73 m  (measured at V1).	Case by case
PD#17.	Use of the following prohibited medication or treatments during study participation: calcium channel blockers (CCBs) if used for the treatment of PAH in vasoreactive patients; drugs containing a catechol group that is metabolised by DβH e.g. rimiterole, isoprenaline, dopamine, dopexamine or dobutamide or α- and/or β-blockers.	Case by case
PD#18.	Current or previous (within the past year) alcohol or substance abuse excluding caffeine or nicotine.	Minor
PD#19.	Presence of any other significant or progressive/unstable medical condition that, in the opinion of the investigator, would compromise evaluation of the study treatment or may jeopardise the patient's safety, compliance or adherence to protocol requirements.	Case by case
PD#20.	
For women: Pregnancy or breast-feeding. Women of childbearing potential (as defined in Section 4.2) unable or unwilling to undergo pregnancy tests and practice highly effective contraceptive measures in combination with a barrier method e.g. condom (without spermicidal foam/gel/film/cream/suppository or fat- or oil-containing lubricants), occlusive cap (diaphragm or cervical/vault caps) with spermicidal gel/film/cream/suppository from the time of informed consent until 30 days after last IMP intake. Highly effective methods for women are surgical intervention (e.g. bilateral tubal occlusion), non-hormonal implantable intrauterine device, true sexual abstinence (i.e. when this is in line with the preferred and usual lifestyle of the patient) and vasectomised partner (provided that the partner is the sole sexual partner of the patient and the partner has received medical assessment of the surgical success). Periodic abstinence (e.g. calendar, ovulation, symptothermal, post-ovulation methods), hormonal contraceptives and withdrawal are not acceptable methods of contraception.
 
For men: Male patients who are sexually active with a partner of childbearing potential must use, with their partner, a condom plus an approved acceptable contraceptive measure from the time of informed consent until 90 days after the last IMP intake. The following methods are acceptable methods of contraception: partner's use of combined (oestrogen and progestogen-containing) hormonal contraception associated with inhibition of ovulation (oral, intravaginal, transdermal); partner's use of progestogen-only hormonal contraception (oral, injectable/implantable,
	Minor

No.	Exclusion Criteria Deviation	Major/ Minor/ Case by case review
	
intrauterine hormone-releasing system); partner's use of implantable intrauterine device; surgical sterilisation (for example, vasectomy or bilateral tubal occlusion).
	
	
Protocol Version Final 2.0: For women: Pregnancy or breast-feeding. Women of childbearing potential unable or unwilling to undergo pregnancy tests and practice acceptable contraceptive measures from the time of informed consent until 30 days after last IMP intake. Acceptable methods for women are surgical intervention (e.g. bilateral tubal occlusion), non-hormonal implantable intrauterine device, double-barrier methods, true sexual abstinence (i.e. when this is in line with the preferred and usual lifestyle of the patient) and vasectomised partner (provided that the partner is the sole sexual partner of the patient and the partner has received medical assessment of the surgical success). Periodic abstinence (e.g., calendar, ovulation, symptothermal, post-ovulation methods), hormonal contraceptives and withdrawal are not acceptable methods of contraception. For men: Male patients who are sexually active with a partner of childbearing potential must use, with their partner, a condom plus an approved acceptable contraceptive measure from the time of informed consent until 90 days after the last IMP intake. The following methods are acceptable methods of contraception: partner's use of combined (oestrogen and progestogen-containing) hormonal contraception associated with inhibition of ovulation (oral, intravaginal, transdermal); partner's use of progestogen-only hormonal contraception (oral, injectable/implantable, intrauterine hormone-releasing system); partner's use of implantable intrauterine device; surgical sterilisation (for example, vasectomy or bilateral tubal occlusion).
	
	
Protocol Version Final 1.0: For women: Pregnancy or breast-feeding. Women of childbearing potential unable or unwilling to undergo pregnancy tests and practice acceptable contraceptive measures. Acceptable methods for women are surgical intervention (e.g. bilateral tubal occlusion), intrauterine device, double-barrier methods and true sexual abstinence (i.e. when this is in line with the preferred and usual lifestyle of the patient). Periodic abstinence (e.g., calendar, ovulation, symptothermal, post-ovulation methods) and withdrawal are not acceptable methods of contraception.
	
PD#21.	Previous participation in any other drug investigational study within the past 30 days (or five half-lives of investigational medicinal product [IMP] whichever is longer) prior to V1.	Case by case
PD#22.	Vulnerable patients according to Section 1.61 of the ICH guideline for Good Clinical Practice E6	Minor

